6.4.2. Secondary Efficacy Analyses

(i) Transplant-Related Mortality (TRM) for Non-Malignant patients or Non-Relapse Mortality (NRM) for Malignant patients at 100 and 180 days

This analysis is intended to characterize the contribution of Time-to-Transplant-Related Mortality (TRM) or Non-Relapse Mortality (NRM) to the composite EFS endpoint. TRM/NRM will be estimated using a Nelson-Aalen cumulative incidence function at days 100 and 180. An event for this endpoint is death without evidence of disease recurrence. Recurrence of disease or relapse will be considered a competing event. Cumulative incidence plots with descriptive summary statistics including incidence and 95% confidence intervals will be presented. If there is sufficient data, the analysis may be repeated by type of disease (malignant or non-malignant).

(ii) Cumulative Incidence and Severity of grade 2-4 acute organ GvHD and moderate - severe chronic GvHD at 180 days

This analysis is intended to characterize the contribution of acute or chronic GvHD to the composite EFS endpoint. Severity of acute and chronic GvHD will be summarized and further in the analysis of safety data. Cumulative incidence of GvHD at day 180 will be estimated from time of transplant using a Nelson-Aalen cumulative incidence function and treating death prior to GvHD as a competing risk.

Cumulative incidence plots with descriptive summary statistics including incidence and 95% confidence intervals will be presented. If there is sufficient data, the analysis will be repeated for each type of disorder (malignant or non-malignant) stratification.

Depending on the number of events, additional GvHD severity subgroups to be analysed include acute grade 1-4 GvHD, grade 2-4 GvHD including skin-only presentation, grade 3-4 GvHD, mild-severe chronic GvHD, and, severe chronic GvHD. The same statistical methods and summary statistics described above will be applied to these analyses.

(iii) Time to Resolution of Acute or Chronic GvHD After Administration of Rimiducid (including Response to Rimiducid)

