Additional cell types and analytes for quantitative immunophenotyping include the absolute and relative numbers of CD3+CD19+ T cells (containing iC9), as well as the number of B cells, NK cells, and levels of IgA, IgM and IgG. In order to describe the pharmacodynamic effects of BPX-501 via proliferation of CD3+CD19+ cells, values post-rimiducid may be excluded. A separate analysis will examine CD3+CD19+ levels using the most recent samples available before and after treatment with rimiducid.

(v) *Time to immune reconstitution defined by CD3 count > 500 cells/uL; CD4 > 200 cells/uL or CD8 count of 200 cells/uL*

Time to immune reconstitution will be based on CD3, CD4 or CD8 counts for the defined thresholds above. Events are defined from the time of transplant to the time at which the threshold is achieved, with death considered as competing event. A patient not achieving the threshold T cell count will be censored on the last recorded visit day.

Time to immune reconstitution will be estimated using a Nelson-Aalen cumulative incidence function for each T cell subtype. Parameters estimates will be summarized for all subjects and by disease type (malignant or non-malignant). When estimable, additional summary statistics will include the median, minimum, maximum, the 25th and 75th percentiles of immune reconstitution, along with the number of events and censored observations. A cumulative incidence plot with descriptive summary statistics will be presented along with the number of patients at risk at various time points.

(vi) *Disease-Free/chronic GvHD-Free survival at 180 days*

The disease-free/chronic GvHD-free survival endpoint at 180 days will be assessed on the ITT (FAS) population. Events corresponding to disease-free/chronic GvHD-free survival outcomes include chronic GvHD, disease relapse for malignant subjects, disease recurrence for non-malignant subjects, or death by any cause. For patients with multiple events, the event that occurs first and the corresponding time will be used. Patients who do not experience an event will be censored on the last recorded visit day. Each patient outcome duration will be calculated from the date of transplant.

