Kaplan-Meier techniques will be used to estimate disease-free/chronic GvHD-free survival at day 180. When estimable, additional summary statistics will include the median, minimum, maximum, the 25th and 75th percentiles along with the number of events and censored observations. Kaplan-Meier plots with descriptive summary statistics will be presented along with the number of patients at risk at various time points.

(vii) *Disease status for the following diseases at 180 days:*

- a. Primary immune disorders as determined by CD3 T cell count \geq 500 cells/uL and normal levels of IgA and IgM at 180 days
- b. Haemoglobinopathies as determined by incidence of RBC transfusion independence (TI) and untransfused haemoglobin of \geq 8.5 g/dL at 180 days
Transfusion Independence (TI) is defined as not having received packed red blood cell transfusions for the previous 8 weeks.
- c. Fanconi Anemia as determined by RBC \geq 3,000,000 cells/uL, neutrophil count \geq 1500 cells/uL and platelet count \geq 150,000 at 180 days
- d. Leukemia as determined by relapse-free-survival (RFS) at 180 days

For a)-d) above, cumulative incidence or survival will be assessed within the patient subpopulation defined as having those diseases at baseline. Cumulative incidence events for a.)-c.) are defined from the time of transplant until the event criteria described is achieved. Competing risks for a.)-c.) include any non-recurrence mortality. Events for RFS are defined as time to relapse or death from any cause.

Cumulative incidence for a.)-c.) will be estimated using a Nelson-Aalen cumulative incidence function for each disease subtype. When estimable, additional summary statistics will include the median, minimum, maximum, the 25th and 75th percentiles of immune reconstitution, along with the number of events and censored observations. A cumulative incidence plot with descriptive summary statistics will be presented along with the number of patients at risk various time points.

Kaplan-Meier techniques will be used to estimate RFS in subjects with leukemia. When estimable, additional summary statistics will include the median, minimum, maximum, the 25th and 75th percentiles along with the number of events and censored observations. Kaplan-Meier plots with descriptive summary statistics will be presented along with the number of patients at risk at various time points.

6.4.3. Other Efficacy Analyses:

(i) Time to Relapse in Subjects with Leukemia

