Cumulative incidence of acute leukemia relapse will be estimated from time of transplant using a Nelson-Aalen cumulative incidence function and treating death prior to relapse as a competing risk. Cumulative incidence plots with descriptive summary statistics including incidence and 95% confidence intervals will be presented.

(ii) Time to Neutrophil Engraftment

Events for neutrophil engraftment is defined as the first of three consecutive measurements of an ANC $\geq 500/\mu\text{L}$ following the conditioning regimen induced nadir, starting from Day 0 (day of transplant). A patient that does not achieve the count of ANC $\geq 500/\mu\text{L}$ will be censored at the last assessment date.

Time to neutrophil engraftment will be estimated using a Nelson-Aalen cumulative incidence function. Death will be considered a competing event. Cumulative incidence plots with descriptive summary statistics including median engraftment time and 95% confidence intervals will be presented.

(iii) Time to Platelet Engraftment

Events for platelet engraftment is defined as the first of three consecutive measurements of platelet count $\geq 20,000/\mu\text{L}$ without platelet transfusion support for seven days. A patient that does not achieve the threshold platelet count of $\geq 20,000/\mu\text{L}$ as required will be censored at the last assessment date.

Time to platelet engraftment will be estimated using a Nelson-Aalen cumulative incidence function. Death will be considered a competing event. Cumulative incidence plots with descriptive summary statistics including median engraftment time and 95% confidence intervals will be presented.

(iv) Analysis of Primary and Secondary Graft Failure

Primary graft failure is defined as failure to achieve an absolute ANC ≥ 500 cells/ μ L by Day 30. The proportion of patients experiencing primary graft failure in the first 30 days will be summarized and reported with a 95% confidence interval.

Secondary graft failure is defined as initial neutrophil engraftment followed by a subsequent decline in neutrophil counts to < 500 cells/ μ L which is unresponsive to growth factor therapy. Sustained neutropenia, i.e., neutrophil counts to < 500 cells/ μ L, observed for greater than 30 days from the administration of growth factors will be summarized.

(v) Infectious Complications

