6.7. Additional Exploratory Analyses

Other exploratory subgroup analyses to characterize safety and efficacy activities for BPX-501 may be conducted. These additional exploratory analyses will be decided at the time of final data analysis.

Sparse PK sampling collected from patients that receive rimiducid will be used to determine the concentration time profile of rimiducid in plasma and summarized as described above. Rimiducid plasma concentration data collected from these subjects will be used as part of a population PK modeling and meta-analysis that will be presented in a separate document. Additional PK assessments may be performed as deemed appropriate.

In addition to the pharmacodynamic and translational analyses specified above, further exploratory analyses are planned and will also be presented in separate documents. These analyses include, among others, analysis of CD45RO/CD45RA/CD62L/CCR7, T cell diversity, and thymic function.

The following additional efficacy analyses were not specified in the protocol, but are being proposed in order to assess longer-term outcomes beyond 180 days and to harmonize with other

study protocols investigating the use of BPX-501. The analyses will be conducted in the ITT population, and, possibly, in the PP population as well.

- (i) Transplant-Related Mortality and Non-Relapse Mortality, defined earlier, at 1 year and 2 years from the time of HSCT. TRM and NRM at those time points will be estimated using a Nelson-Aalen cumulative incidence function.
- (ii) Overall Survival, defined as the time from HSCT to death due to any cause, at 180 days, 1 year and 2 years. Overall survival will be analyzed in all patients as well as stratified by disease subtype (malignant and non-malignant). Overall survival at those time points will be estimated using a Kaplan-Meier survival function.
- (iii) Disease-Free Survival, defined as the time from HSCT to disease recurrence or death, whichever occurs first, in subjects with non-malignant disease. DFS will be estimated at 180 days, 1 year and 2 years using a Kaplan-Meier survival function.
- (iv) Relapse-Free Survival, defined as the time from HSCT to disease relapse or death, whichever occurs first, in subjects with malignant disease. RFS will be estimated at 180 days, 1 year and 2 years using a Kaplan-Meier survival function.

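### For every competing-risk analysis the SAP names an estimator, Nelson-Aalen, that does not estimate the quantity it names, a cumulative incidence

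*SAP*

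**What the plan says.** SAP section 6.4.2(i), on TRM/NRM: "TRM/NRM will be estimated using a Nelson-Aalen cumulative incidence function at days 100 and 180". It adds "Recurrence of disease or relapse will be considered a competing event" and plans this output: "Cumulative incidence plots with descriptive summary statistics including incidence and 95% confidence intervals will be presented".

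The label recurs wherever a competing event is declared:

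- 6.4.2(ii), GvHD: "Cumulative incidence of GvHD at day 180 will be estimated from time of transplant using a Nelson-Aalen cumulative incidence function", with death before GvHD competing.
- 6.4.2(v), immune reconstitution: "Time to immune reconstitution will be estimated using a Nelson-Aalen cumulative incidence function for each T cell subtype", with death competing. Medians and quartiles are also planned.
- 6.4.2(vii) a to c, disease status: same label, medians and quartiles planned, and "Competing risks for a.)-c.) include any non-recurrence mortality".
- 6.4.3(i), leukemia relapse: same label, with death before relapse competing.
- 6.4.3(ii) and (iii): "Time to neutrophil engraftment will be estimated using a Nelson-Aalen cumulative incidence function", and likewise for platelets, with death competing and a median engraftment time planned.
- 6.7(i), mortality at 1 and 2 years: "TRM and NRM at those time points will be estimated using a Nelson-Aalen cumulative incidence function".

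The general rule in 6.2.1 offers only Kaplan-Meier or Nelson-Aalen, as appropriate. The SAP gives no formula and never names a competing-risk estimator. Protocol section 10.4.5.4 asks for a cumulative incidence curve of relapse with death as a competing risk and names no estimator. SAP section 2 says that the SAP prevails over the protocols where methods differ.

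**The concern.** Nelson-Aalen adds up events divided by numbers at risk. The sum is a cause-specific cumulative hazard. It is never below the cumulative incidence, and nothing holds it under 1. A cumulative incidence also weights each term by the probability of still being free of every event just before that time. That weight is what accounts for patients removed by the competing event.

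A programmer working from this SAP could therefore output three different things: the hazard, 1 - exp(-hazard), or the Aalen-Johansen estimate. The first would look absurd for common events and be noticed. The second can look plausible and pass.

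The censoring text adds to the doubt. Sections 6.4.2(v) and 6.4.3(ii) and (iii) censor patients who never reach the threshold at their last visit or assessment. They make no exception for patients who died, although the same sections call death a competing event.

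Most exposed are the frequent outcomes, engraftment and T-cell reconstitution, which SAP section 2 gives as intended effects of the product.

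**Working it through.** The plan states no figure that depends on this choice, so there is none to reproduce. It gives no event rates for these endpoints. Every rate below is an assumption, chosen to show a range.

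**Formulas.** Let F1 be the true incidence of the event and F2 that of the competing event at the time point. Here d1 is the number of events at a time, n the number at risk, and S(t-) the probability of being free of both events just before.

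- Nelson-Aalen: H1 = sum of d1/n.
- Aalen-Johansen: F1 = sum of S(t-) × d1/n.
- With proportional cause-specific hazards, continuous event times and no censoring, the total cumulative hazard is -ln(1 - F1 - F2). The event's share of it is F1/(F1 + F2). So H1 = [F1/(F1 + F2)] × [-ln(1 - F1 - F2)].

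**Worked cases.**

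- TRM/NRM, 3% with 3% relapse: 0.5 × 0.0619 = 0.031, an excess of 0.1 point.
- TRM/NRM, 5% with 10% relapse: 0.3333 × 0.1625 = 0.054, an excess of 0.4 point.
- TRM/NRM, 10% with 25% relapse: 0.2857 × 0.4308 = 0.123, an excess of 2.3 points.
- GvHD or relapse, 20% with 5% deaths: 0.8 × 0.2877 = 0.230, an excess of 3.0 points.
- Reconstitution, 70% with 8% deaths: 0.8974 × 1.5141 = 1.36; 1 - exp(-1.36) = 0.74.
- Reconstitution, 70% with 20% deaths: 0.7778 × 2.3026 = 1.79; 1 - exp(-1.79) = 0.83.
- Engraftment, 95% with 2% deaths: 0.9794 × 3.5066 = 3.43.

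**Where the value passes 100%.** H1 = 1 is reached at a true incidence of about 63% with nothing competing, 61% with 5% competing and 59% with 10% competing.

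**Simulation.** The settings were 160 patients (the BPX-501 number in SAP section 4.2), 5% subject to early censoring, and 500 replicates per case. Mean Aalen-Johansen against mean Nelson-Aalen was:

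- 5.0% against 5.3% (true 5%, competing 5%)
- 10.0% against 11.1% (10%, 10%)
- 19.9% against 22.9% (20%, 5%)
- 80.1% against 178.7% (80%, 5%)
- 97.1% against 441% (97%, 2%)

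Nelson-Aalen exceeded 100% in no replicate of the first three cases and in every replicate of the last two.

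**Medians.** A hazard of 0.5 corresponds to an incidence of 1 - exp(-0.5) = 39% when nothing competes. In the 70%/20% case the total hazard at that point is 0.5/0.7778 = 0.643, and the incidence is 0.7778 × (1 - exp(-0.643)) = 37%. A median read where the hazard reaches 0.5 would come too early.

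**The case against.** The strongest reply is that this is a naming slip. The SAP always calls the quantity a cumulative incidence function, declares a competing event for each endpoint, and labels the outputs as incidences with confidence intervals. Its requests for medians and quartiles make sense only on a probability scale. That describes an Aalen-Johansen estimate, which is built from Nelson-Aalen increments. The repetition may be one phrase copied. This reply stands so far as intent goes: no text says that a raw hazard will be reported. It does not remove the need for correction, because the SAP should fix the estimator before analysis and the one it names is the wrong one.

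A second reply is that the large figures assume continuous event times, while T-cell counts are summarized at days 30, 60, 100 and 180. If reconstitution is tied exactly to those days, constant hazards with deaths at their actual dates give about 1.14 and 1.46 instead of 1.36 and 1.79. Then 1 - exp(-1.14) = 0.68, slightly below the assumed 0.70, so the transformed value is not always too high. Visit dates spread by 7 days either way bring the hazards back to roughly the continuous figures. The literal value exceeds 100% in all these versions.

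A reader might also infer from 6.4.2(vii) that patients who die after recurrence are censored as though recovery were still possible. The text does not say so. Its list of competing risks is introduced by a verb that need not be exhaustive, and no such censoring rule is given. What stands is that the handling of those deaths is left unassigned.

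**Conclusion.** The stated method is wrong as worded and should be corrected. The documents do not establish that results will be wrong. A reader might infer that all reported incidences are inflated and may exceed 100%. That follows only if Nelson-Aalen is applied literally, and values above 100% then arise only for frequent events, at a true incidence of roughly 60% or more.

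Under a literal reading and the assumed rates, TRM/NRM would be overstated by about 0.1 to 2.3 points. Reconstitution and engraftment would not be interpretable, and their medians and quartiles would be wrong. These sizes rest on assumed rates, proportional cause-specific hazards and, for reconstitution, event times not tied to the nominal visit days.

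The primary event-free survival endpoint, overall, disease-free and relapse-free survival, and disease-free/chronic-GvHD-free survival all use Kaplan-Meier and are unaffected. The point does bear on the long-term follow-up: protocol section 10.4.5.5 calls for TRM/NRM at 1 and 2 years, and SAP section 6.7(i) gives that analysis the same label.

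**What to change.** 1. In SAP 6.4.2(i), (ii), (v) and (vii) a to c, 6.4.3(i) to (iii) and 6.7(i), replace the Nelson-Aalen label with: Aalen-Johansen cumulative incidence estimator, with its 95% confidence interval. State the interval method.
2. In 6.2.1, add this estimator for endpoints with competing events and limit Nelson-Aalen to cumulative hazards.
3. In 6.4.2(v) and 6.4.3(ii) and (iii), state that a patient who dies before the event counts as a competing event and is not censored.
4. As a secondary clarification, in 6.4.2(vii) name death from any cause as the competing event for a to c, in line with 6.4.2(v) and 6.4.3(ii) and (iii).

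The cost is SAP wording. Data collection, sample size and the primary analysis do not change. It is best done before the analysis is run, because section 7.1 requires a departure from the approved statistical methods to be documented and justified in the clinical study report.
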